5.3.5.12 Patient-Reported Outcome Data

Adverse event reports will not be derived from PRO data by the Sponsor, and safety analyses will not be performed using PRO data. Sites are not expected to review the PRO data for adverse events.

5.4 IMMEDIATE REPORTING REQUIREMENTS FROM INVESTIGATOR TO SPONSOR

Certain events require immediate reporting to allow the Sponsor to take appropriate measures to address potential new risks in a clinical trial. The investigator must report such events to the Sponsor immediately; under no circumstances should reporting take place more than 24 hours after the investigator learns of the event. The following is a list of events that the investigator must report to the Sponsor within 24 hours after learning of the event, regardless of relationship to study drug:

- Serious adverse events (defined in Section 5.2.2; see Section 5.4.2 for details on reporting requirements)
- Adverse events of special interest (defined in Section 5.2.3; see Section 5.4.2 for details on reporting requirements)
- Pregnancies (see Section 5.4.3 for details on reporting requirements)
- Accidental overdoses or medication errors see Section 5.4.4 for details on reporting requirements)

The investigator must report new significant follow-up information for these events to the Sponsor immediately (i.e., no more than 24 hours after becoming aware of the information). New significant information includes the following:

- New signs or symptoms or a change in the diagnosis
- Significant new diagnostic test results
- Change in causality based on new information
- Change in the event's outcome, including recovery
- Additional narrative information on the clinical course of the event

Investigators must also comply with local requirements for reporting serious adverse events to the local health authority and IRB/EC.

5.4.1 Emergency Medical Contacts

To ensure the safety of study participants, access to the Medical Monitors is available 24 hours per day, 7 days per week. Details will be provided separately. To ensure the

safety of study patients, an Emergency Medical Call Center Help Desk will access the Roche Medical Emergency List, escalate emergency medical calls, provide medical translation service (if necessary), connect the investigator with a Roche Medical Responsible (listed above and/or on the Roche Medical Emergency List), and track all calls. The Emergency Medical Call Center Help Desk will be available 24 hours per day, 7 days per week. Toll-free numbers for the Help Desk, as well as Medical Monitor and Medical Responsible contact information, will be distributed to all investigators.

5.4.2 Reporting Requirements for Serious Adverse Events and Adverse Events of Special Interest

5.4.2.1 Events That Occur prior to Study Drug Initiation

After informed consent has been obtained but prior to initiation of study drug, only serious adverse events caused by a protocol-mandated intervention should be reported. The paper Clinical Trial Adverse Event/Special Situations Form provided to investigators should be completed and submitted to the Sponsor or its designee immediately (i.e., no more than 24 hours after learning of the event), either by faxing or by scanning and emailing the form using the fax number or email address provided to investigators.

5.4.2.2 Events That Occur after Study Drug Initiation

After initiation of study drug, serious adverse events and adverse events of special interest will be reported *throughout the study duration*. Investigators should record all case details that can be gathered immediately (i.e., within 24 hours after learning of the event) on the Adverse Event eCRF and submit the report via the electronic data capture (EDC) system. A report will be generated and sent to Roche Safety Risk Management.

In the event that the EDC system is unavailable, the paper Clinical Trial Adverse Event/Special Situations Form provided to investigators should be completed and submitted to the Sponsor or its designee immediately (i.e., no more than 24 hours after learning of the event), either by faxing or by scanning and emailing the form using the fax number or email address provided to investigators. Once the EDC system is available, all information will need to be entered and submitted via the EDC system.

Instructions for reporting post-study adverse events are provided in Section [5.6](#).

5.4.3 Reporting Requirements for Pregnancies

5.4.3.1 Pregnancies in Female Patients

Female patients of childbearing potential will be instructed through the Informed Consent Form to immediately inform the investigator if they become pregnant during the study. A paper Clinical Trial Pregnancy Reporting Form should be completed and submitted to the Sponsor or its designee immediately (i.e., no more than 24 hours after learning of the pregnancy), either by faxing or by scanning and emailing the form using the fax number or email address provided to investigators. Pregnancy should not be recorded on the Adverse Event eCRF. The investigator should discontinue study drug and counsel the patient, discussing the risks of the pregnancy and the possible effects on the fetus.

Monitoring of the patient should continue until conclusion of the pregnancy. Any serious adverse events associated with the pregnancy (e.g., an event in the fetus, an event in the mother during or after the pregnancy, or a congenital anomaly/birth defect in the child) should be reported on the Adverse Event eCRF. In addition, the investigator will submit a Clinical Trial Pregnancy Reporting Form when updated information on the course and outcome of the pregnancy becomes available. Information regarding child health up to 1 year should be collected on the infant health questionnaire (see [Appendix 13](#)).

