4.1.1 Inclusion Criteria

Patients must meet the following criteria for study entry:

- Ability to provide written informed consent and be compliant with the study protocol
- Diagnosis of PPMS in accordance with the McDonald criteria (Thompson et al. 2017)
- Age 18–65 years at time of signing Informed Consent Form
- EDSS score at screening and baseline ≥ 3.0 to 8.0, inclusive
- Disease duration from the onset of MS symptoms relative to randomization date:

Less than 20 years in patients with an EDSS score at screening 7.0–8.0

Less than 15 years in patients with an EDSS score at screening 5.5–6.5

Less than 10 years in patients with an EDSS score at screening ≤ 5.0

- Documented history or presence at screening of at least one of the following laboratory findings in a CSF specimen (source documentation of laboratory results and method must be verified)

Elevated IgG index

One or more IgG oligoclonal bands detected by isoelectric focusing

- Screening and baseline 9-HPT completed in > 25 seconds (average of the two hands)
- Ability to complete the 9-HPT within 240 seconds with each hand at screening and baseline
- Neurological stability for ≥ 30 days prior to baseline
- Patients previously treated with immunosuppressants, immunomodulators, or other immunomodulatory therapies must undergo an appropriate washout period according to the local label of the immunosuppressant/immunomodulatory drug used

Patients screened for this study should not be withdrawn from therapies for the sole purpose of meeting eligibility for the trial. Patients who discontinue their current therapy for non-medical reasons should specifically be informed before deciding to enter the study of their treatment options and, that by participating in this study, they may be randomized to placebo for a period of 120 weeks or greater.

- For women of childbearing potential: agreement to remain abstinent (refrain from heterosexual intercourse) or use adequate contraceptive methods during the

treatment period and for 6 or 12 months (as applicable by the Ocrevus local label) after the final dose of ocrelizumab.

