4.5.11 Laboratory, Biomarker, and Other Biological Samples

Samples for the following laboratory tests will be sent to the central laboratory for analysis unless otherwise indicated (further details will be provided in the laboratory manual).

- Hematology: hemoglobin, hematocrit, RBC, WBC (absolute and differential: neutrophils, eosinophils, basophils, monocytes, lymphocytes, other cells), and quantitative platelet count
- Blood chemistry: AST, ALT, gamma-glutamyl transferase, total bilirubin, creatinine, amylase, potassium, sodium
- Flow cytometry: Analysis will include, but is not limited to, the determination of the duration of B-cell depletion and recovery (CD19+), B-cell subsets (e.g., CD19, CD27, IgD, CD38 markers to assess naive, memory, plasmablasts and/or other populations), and T-cell counts (CD3+, CD4+, CD8+).
- Quantitative Ig: Ig levels (IgG, IgM, and IgA)

ADA: Serum samples will be collected for determination of antibodies against ocrelizumab. Because ocrelizumab concentrations affect the ADA assay, the concentration of ocrelizumab will be measured as well at all timepoints with ADA assessment to enable interpretation of the results. Refer to [Appendix 1](#), [Appendix 2](#), [Appendix 3](#), and [Appendix 4](#) for details.

- Urinalysis: A urine dipstick will be performed at the site (pH, specific gravity, glucose, protein, ketones, blood), and a microscopic examination if abnormal and clinically significant will be performed at the site (local laboratory).
- Pregnancy test: All women of childbearing potential will have a serum pregnancy test at screening.

All women of childbearing potential must have regular pregnancy tests. A urine pregnancy test (sensitivity of at least 25 mU/mL β -hCG) will be performed locally at the timepoints shown in [Appendix 1](#), [Appendix 2](#), [Appendix 3](#), and [Appendix 4](#). On infusion visits, the urine pregnancy test should be performed prior to the methylprednisolone infusion. A positive urine pregnancy test should be confirmed with a serum test through

the central laboratory prior to any further dosing with study drug. If a urine pregnancy test is positive, the patient will not receive the scheduled dose, and a confirmatory serum pregnancy test will be performed by the central laboratory.

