5.5 FOLLOW-UP OF PATIENTS AFTER ADVERSE EVENTS

5.5.1 Investigator Follow-Up

The investigator should follow each adverse event until the event has resolved to baseline grade or better, the event is assessed as stable by the investigator, the patient is lost to follow-up, or the patient withdraws consent. Every effort should be made to follow all serious adverse events considered to be related to study drug or trial-related procedures until a final outcome can be reported.

During the study period, resolution of adverse events (with dates) should be documented on the Adverse Event eCRF and in the patient's medical record to facilitate source data verification.

All pregnancies reported during the study should be followed with a Pregnancy Outcome and Infant Health Information on First Year of Life questionnaire provided by the Sponsor.

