- ^a Laboratory and safety assessments performed during clinical visit at 24 weeks. All patients will continue in the FU2 for 24 weeks after the last visit either in DBT, OLE, PDP OCR or FU1 phases wherever patient was at that time. For information regarding FU2 duration and eligibility, refer to Section 3.1.1.6.
- ^b At the end of FU2 phase the patient will complete the study.
- ^c Perform a limited, symptom-directed examination at specified timepoints or as clinically indicated. Record new or worsened clinically significant abnormalities on the Adverse Event eCRF.

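### Pregnancy notification stops at study exit, which under a 12-month label normally falls about 4 to 6 weeks before the protocol's own contraception period ends

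*Protocol*

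**What the plan says.** **Notification and follow-up.** Protocol Section 5.4.3.1 has patients told, through the consent form, "to immediately inform the investigator if they become pregnant during the study". Section 5.5.1 adds: "All pregnancies reported during the study should be followed with a Pregnancy Outcome and Infant Health Information on First Year of Life questionnaire". Once a pregnancy has been reported, Section 5.4.3.1 requires monitoring until it concludes and collection of child health data up to 1 year.

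**End of participation.** Appendix 4, footnote a: "All patients will continue in the FU2 for 24 weeks after the last visit either in DBT, OLE, PDP OCR or FU1 phases". Footnote b: "At the end of FU2 phase the patient will complete the study". Section 3.1.1.6 also counts FU2 from the last visit.

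**Post-dose period.** Section 4.1.1 requires contraception during the "treatment period and for 6 or 12 months (as applicable by the Ocrevus local label) after the final dose of ocrelizumab". The pregnancy-intent exclusion (4.1.2) and the open-label extension (OLE) criteria (4.1.3) use the same 6 or 12 months.

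**Other reporting duties.** Section 5.4 lists pregnancies among events that "the investigator must report to the Sponsor within 24 hours after learning of the event, regardless of relationship to study drug", with no end date in that sentence. Spontaneous abortion (5.4.3.2) and congenital anomaly (5.4.3.3) are serious adverse events. Section 5.5.2 keeps related serious adverse events reportable without time limit, even after study closure.

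**The concern.** The protocol defines a period after the last ocrelizumab dose in which it wants pregnancy avoided, but it asks about pregnancy only until study exit. The two periods have different anchors: the contraception period runs from the last dose, FU2 from the last visit. Whether exit comes before the end of the contraception period therefore depends on the label and on how long after the last dose the last visit falls.

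The protocol itself gives reasons to want these cases. Section 5.1.1.1 notes possible B-cell depletion in infants exposed during pregnancy, and reports a median of 72 weeks (range 27 to 175) to B-cell repletion after the last infusion in a Phase II study. Section 4.3.2.3 says that well-controlled data in pregnancy are insufficient. Appendix 13 exists to collect pregnancy outcome and first-year infant health. If an exposed woman conceives after exit but within the contraception period, nobody has asked her to say so, and the questionnaire is not triggered.

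**Working it through.** **Inputs**
- FU2 length: 24 weeks from the last visit (Section 3.1.1.6; Appendix 4, footnote a).
- Contraception period W: 6 months = 182.6 days = 26.1 weeks, or 12 months = 365.25 days = 52.2 weeks, from the final ocrelizumab dose (Section 4.1.1).
- Double-blind phase: six doses 24 weeks apart, so the last is at Week 120; last visit at Week 144 (Table 3; Appendix 1, footnote d).
- OLE: a visit 22 weeks after each dose from the first onward (Appendix 3). The protocol does not fix the lag from last OLE dose to last visit, so it is varied below.

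**Formula.** Let L be the weeks from last dose to last visit. Exit falls at L + 24 weeks after the last dose. Gap = max(0, W − (L + 24)).

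**Check against a stated figure.** A double-blind completer who does not enter the OLE ends FU2 at Week 144 + 24 = 168, that is 168 − 120 = 48 weeks after the last dose. This equals the 48 weeks that Section 5.6 gives for the adverse event reporting period.

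**Results**

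| L (weeks) | Situation | Exit after last dose | Gap, 6-month label | Gap, 12-month label |
|---|---|---|---|---|
| 24 | End of a full dosing interval | 48 weeks | 0 | 52.2 − 48 = 4.2 weeks |
| 22 | OLE visit 22 weeks after dose | 46 weeks | 0 | 52.2 − 46 = 6.2 weeks |
| 12 | Last visit 12 weeks after dose (illustrative) | 36 weeks | 0 | 52.2 − 36 = 16.2 weeks |
| 0 | Last visit is the dosing visit (limiting case) | 24 weeks | 26.1 − 24 = 2.1 weeks | 52.2 − 24 = 28.2 weeks |

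The ±7-day window on the FU2 visit moves each non-zero gap by 1 week.

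**Break-even.** The 6-month period is fully covered once L is at least 26.1 − 24 = 2.1 weeks. The 12-month period is covered only if L is at least 52.2 − 24 = 28.2 weeks, for example after a long follow-up 1 (FU1) phase.

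**What other duties catch after exit.** Section 5.4.3.1 keeps pregnancy itself off the adverse event form. Sections 5.5.2 and 5.6 cover related serious adverse events, so they can catch a related congenital anomaly or miscarriage. They do not catch an uneventful pregnancy with a live birth, nor an infant infection that is non-serious or judged unrelated. Section 5.4 applies once the investigator learns of a pregnancy, but no text in the protocol asks the former patient to report one.

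**The case against.** The strongest reply is that the safety net is wider than it looks. Section 5.4 puts no end date on reporting a pregnancy the investigator learns of, and related serious adverse events stay reportable indefinitely. This stands. A reader might infer that exposed pregnancies after exit go unreported altogether; the documents do not support that. Nor do they support reading infant follow-up as stopping at study end: a pregnancy already reported is followed to its conclusion and the child to 1 year.

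The size is also easy to overstate. One might take 24 weeks of FU2 against 6 or 12 months and conclude that every woman has a gap of up to 28 weeks. The two periods start at different points, and the 28-week figure needs the last visit to be the dosing visit itself, although early stoppers are meant to return for a separate discontinuation visit. Women who received only placebo have no ocrelizumab-exposed pregnancy, and the contraception wording runs from the final ocrelizumab dose.

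The 6 or 12 months is a contraception period by local label, and nothing in the protocol says that pregnancy surveillance must match it. That is fair: this is a design choice, not a contradiction. Likewise, Appendix 13 asks for infant CD19 counts only in its infection tables, so no general infant B-cell dataset is being lost, and the advice on infant live vaccines in Section 5.1.1.1 stands whether or not a form is filed.

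Shortening FU2 to 24 weeks was deliberate, with a stated rationale (established safety profile, earlier access to post-study treatment). The point here does not require a longer FU2. Finally, the consent form is not available for this review and may already carry post-study instructions.

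These replies narrow the point without removing it: none reaches an uneventful exposed pregnancy that the woman has not been asked to report.

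**Conclusion.** The point holds in a limited form. For ocrelizumab-exposed women under a 12-month label who exit on schedule, about the last 4 to 6 weeks of the contraception period fall outside pregnancy solicitation and follow-up. After early discontinuation of OLE or post-double-progression ocrelizumab (PDP OCR) the gap grows as the last visit moves closer to the last dose, with a limit of about 28 weeks (12-month label) or 2 weeks (6-month label). Under a 6-month label there is normally none.

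The loss is confined to solicitation and infant follow-up of otherwise uneventful exposed pregnancies. The result assumes that the last visit falls 22 to 24 weeks after the last dose on the normal path, that FU2 is completed, and that the consent form does not already extend notification. Women who withdraw before completing FU2 could have a longer gap. The number of women affected is not stated in the documents, so no count of missed cases can be given.

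**What to change.** In Protocol Sections 5.4, 5.4.3.1 and 5.5.1, and in the consent form if it has the same wording, extend pregnancy notification and the infant questionnaire to the end of the protocol's existing 6- or 12-month period after the final ocrelizumab dose. By construction this closes the gap under either label. The cost is wording plus occasional pregnancy forms after study exit; there are no added visits and FU2 keeps its length.

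Two neighbouring inconsistencies should be reconciled in the same amendment:
- **Pregnancy testing.** Section 4.5.11 states "All women of childbearing potential must have regular pregnancy tests" and refers to timepoints in Appendices 1 to 4. Appendix 4 lists no pregnancy test, and the FU1 follow-up column of Appendix 2 is blank for it. This may be only a stock cross-reference, and a test at the final FU2 visit would not detect later conceptions, so it is separate from the gap above.
- **Adverse event reporting period.** Section 5.6 ends it 48 weeks after the last dose; Section 5.5.2 has collection run through the end of FU2. The two coincide only when the last visit falls 24 weeks after the last dose.

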5.4.3.2 Abortions

A spontaneous abortion should be classified as a serious adverse event (as the Sponsor considers abortions to be medically significant), recorded on the Adverse Event eCRF, and reported to the Sponsor immediately (i.e., no more than 24 hours after learning of the event; see Section [5.4.2](#)).

If a therapeutic or elective abortion was performed because of an underlying maternal or embryofetal toxicity, the toxicity should be classified as a serious adverse event, recorded on the Adverse Event eCRF, and reported to the Sponsor immediately (i.e., no more than 24 hours after learning of the event; see Section [5.4.2](#)). A therapeutic or elective abortion performed for reasons other than an underlying maternal or embryofetal toxicity is not considered an adverse event.

All abortions should be reported as pregnancy outcomes on the paper Clinical Trial Pregnancy Reporting Form.

5.4.3.3 Congenital Anomalies/Birth Defects

Any congenital anomaly/birth defect in a child born to a female patient exposed to study drug should be classified as a serious adverse event, recorded on the Adverse Event eCRF, and reported to the Sponsor immediately (i.e., no more than 24 hours after learning of the event; see Section [5.4.2](#)).

5.4.4 Reporting Requirements for Cases of Accidental Overdose or Medication Error

Accidental overdose and medication error (hereafter collectively referred to as "special situations"), are defined as follows:

- Accidental overdose: accidental administration of a drug in a quantity that is higher than the assigned dose
- Medication error: accidental deviation in the administration of a drug

In some cases, a medication error may be intercepted prior to administration of the drug.

Special situations are not in themselves adverse events but may result in adverse events. Each adverse event associated with a special situation should be recorded separately on the Adverse Event eCRF. If the associated adverse event fulfills

seriousness criteria or qualifies as an adverse event of special interest, the event should be reported to the Sponsor immediately (i.e., no more than 24 hours after learning of the event; see Section 5.4.2). For ocrelizumab or matching placebo, adverse events associated with special situations should be recorded as described below for each situation:

- Accidental overdose: Enter the adverse event term. Check the "Accidental overdose" and "Medication error" boxes.
- Medication error that does not qualify as an overdose: Enter the adverse event term. Check the "Medication error" box.
- Medication error that qualifies as an overdose: Enter the adverse event term. Check the "Accidental overdose" and "Medication error" boxes.

In addition, all special situations associated with ocrelizumab or matching placebo, regardless of whether they result in an adverse event, should be recorded on the Adverse Event eCRF as described below:

- Accidental overdose: Enter the drug name and "accidental overdose" as the event term. Check the "Accidental overdose" and "Medication error" boxes.
- Medication error that does not qualify as an overdose: Enter the name of the drug administered and a description of the error (e.g., wrong dose administered, wrong dosing schedule, incorrect route of administration, wrong drug, expired drug administered) as the event term. Check the "Medication error" box.
- Medication error that qualifies as an overdose: Enter the drug name and "accidental overdose" as the event term. Check the "Accidental overdose" and "Medication error" boxes. Enter a description of the error in the additional case details.
- Intercepted medication error: Enter the drug name and "intercepted medication error" as the event term. Check the "Medication error" box. Enter a description of the error in the additional case details.

As an example, an accidental overdose that resulted in a headache would require two entries on the Adverse Event eCRF, one entry to report the accidental overdose and one entry to report the headache. The "Accidental overdose" and "Medication error" boxes would need to be checked for both entries.

